Low carbohydrate diet is a diet plan which stresses on reducing carbohydrate intake to less than 20g daily. Numerous studies have shown that weight loss could be obtained by reduction of calorie intake in either the form of carbohydrate or fat. CKD patients are recommended to consume low protein diet of less than 0.6-0.7g/kg/day with little emphasis on calorie or carbohydrate intake.

This study, thus, aims to evaluate the effects of low carbohydrate and moderate fat (LCBD) in addition to low protein diet on renal disease in patients with DKD.

Objectives

1. To evaluate the effects of LCBD in comparison to low protein diet (LPD) alone on renal outcome in patients with DKD
2. To evaluate the effects of LCBD in comparison to low protein diet (LPD) alone on anthropometric and other metabolic parameters in patients with DKD
3. To determine the associations between renal outcome and metabolic parameters in patients with DKD who received LCBD and standard therapy.

OUTCOME MEASURES

Primary Outcome

1. Proteinuria as assessed by UACR
2. Rise in serum creatinine, reduction in eGFR

Secondary Outcomes

- 1. Weight loss, blood pressure**
- 2. Metabolic parameters- lipid profile and inflammatory markers including hsCRP, IL-6**

HYPOTHESES

LCBD reduces proteinuria and improves renal function compared to standard treatment in patients with DKD.

LCBD causes significant weight loss and improvement in other metabolic parameters compared to standard treatment in patients with DKD.

Study Design

This is an investigator-initiated, single centre, randomized, controlled, clinical trial in Type 2 diabetes mellitus patients, comparing 12-weeks of LCBD compared to standard medical therapy in patients with DKD.

Patient Selection

Recruitment would be conducted at the Endocrinology and Nephrology clinics of UiTM. Patients with Type 2 Diabetes Mellitus undergoing follow-up in these clinics who meet the inclusion and exclusion criteria will be invited to participate in the study.

Inclusion Criteria

1. Diagnosed with Type 2 DM of more than 5 years
2. Diagnosis of stable CKD of more than 6 months
3. HbA1c of 7% - 10.5%
4. Patient age between 40-75 years old
5. Able to sign informed consent

Exclusion Criteria

1. Type 1 DM
2. Frequent hypoglycemia
3. Persistent elevations of serum liver transminase

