4. Heart failure (New York Heart Association functional class III-IV), active systemic inflammatory disease, chronic renal failure requiring hemodialysis, active hepatic disease and collagen disease
5. Malignancy
6. Recent hospital admission for acute within the past 3 months
7. Pregnant women, breastfeeding or planning to conceive within the next year

All patients who fulfilled the inclusion and exclusion criteria will be offered to participate in the study and written consent will be obtained.

SAMPLE SIZE CALCULATION

This is a single centre, interventional, randomised, controlled clinical trial. This will be a pilot study involving 20 patients per arm. However, considering a **20% dropout, we would be recruiting 24 patients per arm.**

STATISTICAL ANALYSIS

The SPSS program will be used for the statistical analysis. Differences between before and after intervention will be analyzed by employing one-way ANOVA, following unpaired t-test. A Pearson's correlation analysis would be carried out to determine the correlation of the changes of proteinuria, creatinine, weight loss, and other variables. levels and surrogate endothelial function marker.

STUDY PROTOCOL

Following informed consent, patients would be randomised to either LCBD or low protein Diet (LPD) group.

All recruited patients will be given the standard dietary and exercise advice which will include low protein of 0.6-0.7g/kg/day and low salt diet.

In addition, patients within the LCBD will be given a prescription diet of 20g of carbohydrate daily. This will be supplemented by visual aids on carbohydrate counts of various local food. Patients would be given the option to choose their most appropriate food types which will amount to the carbohydrate count given. Patients on oral anti-diabetic treatment including insulin will be advised on titrations of their medications to avoid hypoglycaemia.

The control arm will not be given any additional advice.

All patients will be required to fill in a 3day food diary during their scheduled visits which will be at 6 weeks and 12 weeks.

Clinical assessments include blood sampling which will be done at baseline and at study end.

ULTRASOUND FOR FATTY LIVER

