4. B. Goh, L. Ong, Y. LimTwenty First Report of the Malaysian Dialysis and Transplant 2013. Malaysian Society of Nephrology, Kuala Lumpur, Malaysia (2014)
6. Australian Radiation Protection and Nuclear Safety Agency. Ionizing Radiation and Health. Updated 3 December 2003. <https://www.legislation.gov.au/Details/F2019C00829>

FLOWCHART

Effects of Low Carbohydrate Diet (LCBD) on Weight and Renal Outcome in Patients with Diabetic Kidney Disease (DKD)- A pilot study
Revised Budget

No	Item	Price per item (RM)	Quantity	Total (RM)
1	Fasting plasma glucose	15	96	1,440
2	HbA1c	25	96	2,400
3	Lipid profile	15	96	1,440
4	Liver profile	15	96	1,440
5	Renal profile	15	96	1,440
6	UPCI	15	96	1,440
6	ELISA kits for surrogate markers hsCRP	2000/kit	2	4,000
7	ELISA kits for IL-6	3000/kit	2	6,000
8	Insulin (for 100 tests)	2,350	1	2,350
9	Glucometer and strips	200	48	9,600
10	Patient reimbursement	50/ visit	50 x 9 x 24 = 50 x 7 x 24	10,800 + 8,400 = 19,200
11	USS (Fatty liver)	50	96	4,800
12	Dexa	190	96	19,200
10	Stationery + Visual Aids	50/patient	48	2,400
			TOTAL	76,950

Gaant Chart

See Appendix A

Key Milestones

Milestone	Timeline	Milestone description
Ethics Approval	Sept 2018	Starting of recruitment
Patient Recruitment	Dec 2018	50% recruitment
	March 2019	100% recruitment
Patient randomisation	Dec 2018 Blood sampling and other measurements	50%
	April 2019	100% randomised
Data Compilation	Jul 2019	100% data compilation
Data Analysis and interpretation	Sept 2019	Completed data collection and performing Statistical analysis
Report Writing	Dec 2019	Completed report writing
Submission report	Feb 2020	Submission completed

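### Does the budget's split of 9 and 7 paid visits mean the two arms get unequal contact, so that the diet comparison needs redesign?

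*Combined protocol and SAP*

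**What the plan says.** The STUDY PROTOCOL section describes one schedule without distinguishing the arms. Every patient completes a 3-day food diary at "scheduled visits which will be at 6 weeks and 12 weeks". The next sentence adds: "Clinical assessments include blood sampling which will be done at baseline and at study end". Read together, these give baseline, week 6 and week 12.

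The same section makes the difference in content explicit. LCBD patients get a carbohydrate prescription and visual aids, whereas "The control arm will not be given any additional advice". Patients on glucose-lowering treatment "will be advised on titrations of their medications to avoid hypoglycaemia"; the text does not say at which contacts this happens.

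The Revised Budget enters patient reimbursement, at RM 50 per visit, as "50 x 9 x 24 = 50 x 7 x 24", with the total "10,800 + 8,400 = 19,200". It does not name the two groups of 24 or define a paid visit. The SAMPLE SIZE CALCULATION section says "we would be recruiting 24 patients per arm".

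The first objective is "To evaluate the effects of LCBD in comparison to low protein diet (LPD) alone on renal outcome in patients with DKD".

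**The concern.** Neither 9 nor 7 fits a schedule of three time points. The group size of 24 equals the planned recruitment per arm, so the natural reading is that one arm attends, and is paid for, two more visits per patient than the other.

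That could matter for interpretation. The protocol's introduction says that dietary programmes are limited by adherence and that weight loss attenuates renal disease. Extra contact could improve adherence, then weight (a secondary outcome), then albuminuria and renal function (the primary outcomes). If only one arm had that contact, a difference read as the effect of carbohydrate restriction would be partly an effect of attention. The planned unpaired comparison could not separate the two.

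**Working it through.** **Inputs.** From the Revised Budget: RM 50 per visit, 9 visits for 24 patients, 7 visits for 24 patients. From the SAMPLE SIZE CALCULATION section: 24 per arm, so 48 in all. From the STUDY PROTOCOL section: baseline, week 6 and week 12.

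**Reproducing the budget figure.**
- 50 × 9 × 24 = 10,800
- 50 × 7 × 24 = 8,400
- 10,800 + 8,400 = 19,200, as printed, if the equals sign between the two products is read as a plus.

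**Size of the gap, if the groups are the arms.**
- Patient-visits: 9 × 24 = 216 and 7 × 24 = 168; difference 48, total 384
- Payment per patient: 9 × 50 = RM 450 and 7 × 50 = RM 350
- Cost of the difference: 2 × 24 × 50 = RM 2,400

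**Against the readable schedule.** Three time points for 48 patients give 3 × 48 = 144 patient-visits, or RM 7,200, well short of 384. The remainder is not a measure of a fault in the plan. The sentence about all patients names only weeks 6 and 12, and baseline comes from the sentence on blood sampling. Nothing says that no other contacts occur, and the times of diet teaching and titration advice are not given. The flowchart and Appendix A did not survive the reading of the file. The shortfall therefore reflects in part what can be read here.

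**Could imaging explain the split?** Ultrasound and DEXA each have quantity 96 = 2 × 48, as do most laboratory lines. That fits two assessments for every patient in both arms. Separate imaging days could raise both counts above three, but would not readily produce 9 in one group and 7 in the other. A pooled quantity cannot rule it out.

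**How reliable is the budget?**
- DEXA: 190 × 96 = 18,240, but 19,200 is entered.
- Sum of all lines: 1,440 × 5 + 2,400 + 4,000 + 6,000 + 2,350 + 9,600 + 19,200 + 4,800 + 19,200 + 2,400 = 77,150, but 76,950 is printed.
- The reimbursement cell itself has the misplaced equals sign.

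This is a costing sheet with several slips. It records planned spending and does not prescribe how the arms are to be followed.

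**Effect on the analysis.** Contact given after randomisation as part of an arm does not unbalance the groups at baseline or invalidate the between-arm test. It changes what the difference describes: the diet together with its support, rather than carbohydrate restriction alone. The protocol already sets LCBD plus added advice against an arm with no added advice, and its hypotheses name standard treatment as the comparator.

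**The case for a change.** The strongest case for acting is that the split looks deliberate. Reimbursement is the only line divided into 24 and 24; the other per-patient quantities are pooled at 96 or 48. Both subtotals are correct for 9 and 7 visits, and so is their sum, so the misplaced sign is probably the only slip in that cell. The protocol discloses extra advice in one arm, but the readable text discloses neither extra visits nor extra payment. Matching at 9 visits would cost 9 × 48 × 50 = RM 21,600, which is RM 2,400 more than budgeted and about 3% of the total (2,400 / 76,950 = 3.1%).

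Much of this stands. The sections do not agree, the arms are the most natural reading of the two groups, and the cost is small. It does not establish that equal contact is required. Extra visits in the LCBD arm, if that is where they fall, may serve the titration advice. They would then belong to delivering that diet, and whether to keep them is for the investigator. Equal attendance would isolate the diet more cleanly, but would move the control arm away from standard care. Either choice is defensible in a pilot planned for 20 patients per arm. The documents give no size or direction for any effect of two additional visits.

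**Conclusion.** No change to the design or the statistical analysis follows. The discrepancy is an inconsistency between a budget line and the visit text. It is worth reconciling by labelling the two groups and saying which visits are paid and when, but this is clerical. If the arms do differ in attendance, a competent analyst would report contacts by arm and describe the result as the effect of the LCBD package; the present design and tests allow that.

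At most, the difference is two paid visits per patient (48 patient-visits, RM 2,400). That figure assumes that the line reflects conduct and that the two groups of 24 are the arms. The readable documents confirm neither, and the unreadable flowchart or Appendix A may settle both. Any effect of the extra contact on albuminuria, renal function or weight cannot be quantified from the documents.

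### The budget implies one urine value before and one after treatment; baseline adjustment of log UACR is the main gain available, and a 6-week urine sample adds a little for week 12

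*Combined protocol and SAP*

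**What the plan says.** Outcome Measures lists two primary outcomes, "Proteinuria as assessed by UACR" and "Rise in serum creatinine, reduction in eGFR". Under Study Protocol, "All patients will be required to fill in a 3day food diary during their scheduled visits which will be at 6 weeks and 12 weeks", so all patients have a 6-week visit. The only sentence on sampling times is "Clinical assessments include blood sampling which will be done at baseline and at study end"; it names blood and is silent on urine. The Revised Budget has a single urine line, "UPCI 15 96 1,440", and no line for UACR.

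Statistical Analysis compares changes over the intervention by one-way ANOVA and an unpaired t-test. It mentions no baseline adjustment, repeated-measures model or method for missing data. Sample Size Calculation states "This will be a pilot study involving 20 patients per arm", then adds "20% dropout, we would be recruiting 24 patients per arm"; it gives no effect size, SD, correlation or power.

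**The concern.** With about 20 evaluable patients per arm, a primary urine outcome that rests on one value before and one after leaves little room for noise. An unpaired t-test on change scores also uses the baseline inefficiently: it subtracts the baseline in full, whatever its correlation with the final value. A patient who attends at 6 weeks and then leaves contributes no follow-up urine value, although 20% dropout is expected and no missing-data method is given. At stake are the precision of the UACR comparison and how much this pilot can say about the size and timing of an effect.

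**Working it through.** **The plan's own figures.** 20 x 1.20 = 24 per arm, so 48 in total, as stated. 96 / 48 = 2 urine tests per patient, and 96 x RM15 = RM1,440, as printed. Two per patient fits one before and one after. With 20% dropout, 24 x 0.80 = 19.2 per arm reach week 12 and 4.8 do not.

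**Assumptions, because the documents give none.** Equal variance of log UACR at each visit, set to 1; correlation r between any two visits, range 0.3-0.9; two-sided 5% level and 80% power; the planned t-test read as a between-arm comparison of change scores. The formulas are large-sample and ignore the small cost of estimating the baseline slope.

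**Step 1: baseline adjustment, week 12 as target.** Change-score variance is 2(1 - r) and baseline-adjusted variance is 1 - r². Their ratio is (1 + r)/2.

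**Step 2: add a week-6 value, week 12 still the target.** Completers gain nothing. With monotone dropout the variance ratio is 1 - p²(1 - n12/n6), where p = r/(1 + r) and n12 = 19.2. If all dropouts leave before week 6, n6 = 19.2 and the gain is 0. If half leave after it, n6 = 21.6; if all leave after it, n6 = 24.

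**Step 3: mean of weeks 6 and 12 as target.** Adjusted variance is (1 + r)/2 - r², compared with 1 - r² for week 12 alone. With ratio R, power is lost if the week-6 effect is below 2√R - 1 of the week-12 effect.

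| r | Step 1 cut | Step 2 cut (half / all leave after week 6) | Step 3 cut | Step 3 break-even |
|---|---|---|---|---|
| 0.3 | 35% | 0.6% / 1.1% | 38% | 57% |
| 0.5 | 25% | 1.2% / 2.2% | 33% | 63% |
| 0.7 | 15% | 1.9% / 3.4% | 29% | 68% |
| 0.8 | 10% | 2.2% / 4.0% | 28% | 70% |
| 0.9 | 5% | 2.5% / 4.5% | 26% | 72% |

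Example at r = 0.7. Step 1: 0.51/0.60 = 0.85. Step 2, all leaving after week 6: p = 0.412, and 0.412² x (1 - 0.8) = 0.034. Step 3: 0.36/0.51 = 0.706.

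On unadjusted change scores, averaging takes the variance from 2(1 - r) to 1.5(1 - r), a 25% cut at any r, with break-even 2√0.75 - 1 = 73%. Simulations of 4,000 trials per setting gave Step 3 ratios of 0.65-0.67, 0.70-0.71 and 0.72-0.73 at r = 0.5, 0.7 and 0.8, in line with the formula.

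**Step 4: unequal correlations.** Suppose follow-up visits correlate 0.8 with each other and 0.6 with baseline. The Step 3 ratio is (0.90 - 0.36)/0.64 = 0.84, a 16% cut. With 0.85 and 0.7 it is (0.925 - 0.49)/0.51 = 0.85, a 15% cut. Break-even then rises to 2√0.84 - 1, or about 84%, and to about 85%.

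**Detectable difference at 20 per arm, r = 0.7.** (1.960 + 0.842) x √(2/20) = 0.886. Change score: 0.886 x √0.60 = 0.69 SD. Baseline-adjusted week 12: 0.886 x √0.51 = 0.63 SD.

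**The case against.** The trial calls itself a pilot and makes no power claim, so one value before and one after is a legitimate choice. Recruitment is already raised from 20 to 24 per arm for dropout. A 6-week urine sample does nothing for creatinine and eGFR. These points stand, and they limit this to an improvement worth making, not an error.

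The evidence on timing is also indirect. A reader might infer that the protocol fixes urine at baseline and study end and uses the 6-week visit only for the food diary. The sampling sentence covers blood, so the two-sample reading rests on the budget quantity. The flowchart and Appendix A are not legible in the available text, and the budget reimburses 9 and 7 visits per patient, more than Study Protocol describes. Other activity at week 6 cannot be ruled out.

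A reader might also infer that the extra sample makes 20 per arm worth about 28-30. That is 20/0.72 to 20/0.67. It holds only if the average of the two visits becomes the outcome, all visits correlate equally and the week-6 effect is as large as the week-12 effect. The Introduction offers weight loss as a possible mechanism, so an effect still growing at week 6 is plausible. Nor would the sample cover dropouts in general: it helps only those who leave after week 6, and only under missing-at-random.

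**Conclusion.** The point holds in a limited form. The budget implies two urine values per patient, and the planned test uses them less efficiently than it could. The larger gain that keeps week 12 as the target comes from the analysis: a variance cut of about 15% at r = 0.7 and 25% at r = 0.5, equivalent to 20/0.85 = 23.5 and 20/0.75 = 26.7 patients per arm. The 6-week sample adds about 0-5% to week-12 precision, depending on r and on when patients leave; its other value is on-treatment data from later dropouts and information on the timing of any effect.

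The average of weeks 6 and 12 could cut variance by 28-33% (equal correlations of 0.5-0.8) or by only about 15-16% (follow-up visits more alike). Under equal correlations it loses power if the week-6 effect is below about 57-73% of the week-12 effect, depending on r and the analysis. It should not be primary. All these sizes rest on assumed correlations, since the documents give none.

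**What to change.** 1. State when urine is collected, and reconcile UPCI in the budget with UACR as the primary outcome.
2. Analyse log UACR with a baseline-adjusted model in place of the unpaired t-test on differences, and name the 12-week between-arm contrast as primary. This needs no new data.
3. Collect urine at the existing 6-week visit and fit weeks 6 and 12 in one baseline-adjusted repeated-measures model. State the missing-at-random assumption.
4. Pre-specify the average of weeks 6 and 12 as supportive, and say that it describes the effect over 6-12 weeks.

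Cost: 48 x RM15 = RM720, or 720/76,950 = 0.9% of the stated total, at the UPCI price. If a UACR test cost twice as much, it would be RM1,440, or 1.9%. The budget needs correcting in any case: DEXA is 190 x 96 = RM18,240, not 19,200, and the printed lines sum to RM77,150, not 76,950. With DEXA corrected they sum to RM76,190, which leaves RM760 under the stated total. That covers RM720 but not RM1,440. The 6-week visit is already scheduled; the documents do not show whether it has staff and laboratory time for urine.

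### Hypoglycaemia is a recognised hazard of the 20 g diet and every patient is budgeted a glucometer, but no reading, episode or drug change is planned as trial data

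*Combined protocol and SAP*

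**What the plan says.** **Intervention.** After consent, "patients would be randomised to either LCBD or low protein Diet (LPD) group" (Study Protocol). Both arms receive the low-protein, low-salt advice. In addition, "patients within the LCBD will be given a prescription diet of 20g of carbohydrate daily". The same paragraph continues: "Patients on oral anti-diabetic treatment including insulin will be advised on titrations of their medications to avoid hypoglycaemia". The next sentence gives the control arm no extra advice.

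**Hazard recognised.** Besides the titration sentence, frequent hypoglycaemia is the second exclusion criterion. Neither place defines hypoglycaemia.

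**Equipment.** The Revised Budget has a row "Glucometer and strips": RM200 each, 48 units, RM9,600.

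**Measurement.** "Clinical assessments include blood sampling which will be done at baseline and at study end". The only patient-completed record is a 3-day food diary at the 6-week and 12-week visits.

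**Outcomes.** The primary outcomes are UACR, and serum creatinine with eGFR. The secondary outcomes are weight, blood pressure and "Metabolic parameters- lipid profile and inflammatory markers including hsCRP, IL-6".

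**Analysis.** The Statistical Analysis section names one-way ANOVA, the unpaired t-test and Pearson correlation. It has no summary of events.

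**The concern.** The plan sees the hazard, tells patients to adjust their drugs because of it, and pays for the device that would detect it. The chain stops before anything becomes data. No sentence says when patients test, what they write down, or whether readings come back to the trial.

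Two things are at stake. First, UACR or weight could improve alongside more hypoglycaemia, and the listed outcomes would not show it. Fasting glucose and HbA1c are budgeted at two time points, but neither is a listed outcome, and two samples cannot count episodes over 12 weeks.

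Second, drug changes bear on the efficacy results. The introduction notes that SGLT-2 inhibitors and GLP1 agonists can reduce weight and are of interest for slowing renal disease. If such drugs are altered more in one arm and the change is not recorded, differences in weight and renal outcome are harder to attribute to the diet.

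Episodes and dose changes that nobody writes down cannot be recovered afterwards. A pilot is the natural place to learn how often they occur.

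**Working it through.** **1. Who holds a meter.** The Sample Size section states "This will be a pilot study involving 20 patients per arm" and, after allowance, "20% dropout, we would be recruiting 24 patients per arm".
- 20 × 1.20 = 24, as printed. Dividing by the retained fraction gives 20 / 0.80 = 25; the one-patient difference does not matter here.
- 24 × 2 = 48 patients, and 48 × RM200 = RM9,600, which matches the budget row. There is one meter per recruited patient, in both arms.
- Laboratory rows: 48 × 2 time points = 96 tests, which matches sampling at entry and at the end.

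**2. Where a reading or episode could enter the data.**

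| Place in the plan | Content | Glucose reading, episode or drug change? |
|---|---|---|
| Primary outcomes | UACR; creatinine and eGFR | None |
| Secondary outcomes | Weight, blood pressure, lipids, hsCRP, IL-6 | None |
| Patient record | 3-day food diary, weeks 6 and 12 | None described |
| Blood sampling | Start and end | Two samples, not episodes |
| Analysis | ANOVA, t-test, correlation | No event summary |

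**3. Patients affected.** The documents give no event risk, so this is an assumed range for the 24 low-carbohydrate patients.
- 5%: 0.05 × 24 = 1.2
- 10%: 0.10 × 24 = 2.4
- 20%: 0.20 × 24 = 4.8
- 30%: 0.30 × 24 = 7.2

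That is about 1 to 7 patients. The number taking insulin or other glucose-lowering drugs is not given, so 24 is a ceiling for those at risk.

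**4. What a count would give.** The chance of at least one affected patient is 1 − (1 − p)^24:
- p = 5%: 71%
- p = 10%: 92%
- p = 20%: over 99%

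Exact (Clopper-Pearson) two-sided 95% limits: for 0 of n, the upper limit is 1 − 0.025^(1/n). For x > 0, the limits are the 0.025 quantile of Beta(x, n − x + 1) and the 0.975 quantile of Beta(x + 1, n − x).

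| Affected | 95% interval |
|---|---|
| 0/24 | 0 to 14.2% |
| 0/20 | 0 to 16.8% |
| 2/24 | 1.0% to 27.0% |
| 5/24 | 7.1% to 42.2% |

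**5. Whether the arms could be compared.** Power of Fisher's exact test at 24 per arm, two-sided 5%, with assumed risks in the LPD and LCBD arms:

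| LPD v LCBD | Power |
|---|---|
| 5% v 20% | 24% |
| 10% v 30% | 31% |
| 5% v 30% | 56% |
| 5% v 40% | 82% |

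Only a very large difference would be detected reliably.

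**6. Visits.** The Study Protocol section names follow-up visits at weeks 6 and 12. The reimbursement row prices 50 × 9 × 24 = RM10,800 and 50 × 7 × 24 = RM8,400, together RM19,200. That is nine paid visits for one group of 24 and seven for the other, without saying which group is which or what the visits are for.

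**The case against.** The strongest reply is that silence is not proof of non-use. The opening pages, the flowchart and the content of Appendix A were not available, and a flowchart is a natural place for monitoring. The quoted sentence says that assessments include blood sampling, which does not make the list exhaustive. Home readings may well inform titration. This stands: the point is that the available text states no use of the readings as data, not that nobody looks at them.

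A reader might infer three stronger things, and the documents support none of them.
- **Six weeks without contact.** Week 6 is the first follow-up visit named, but the budget pays for nine and seven visits. Their purpose is undescribed, so they do not prove monitoring, but they rule out treating six weeks as an established gap.
- **A contradiction between the titration sentence and the blood schedule.** Both can be true. Samples at the start and end can serve the laboratory outcomes, while home meters support titration. The fault is under-description.
- **No harm is counted at all.** Worsening creatinine and eGFR is a primary outcome in both arms, and a liver profile is budgeted. The gap concerns hypoglycaemia and drug changes.

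It is also fair to object that raw counts by arm could reflect detection. No blinding is described, the titration advice sits with one arm, and paid visits differ. This does not remove the point, but it governs how the data should be collected.

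**Conclusion.** The point holds in limited form. The available protocol names the hazard and funds a meter for each of 48 patients. It lists no hypoglycaemia outcome and describes no record of episodes or drug changes in either arm. As written, no rate can be produced for either group. The size, about 1 to 7 of 24 LCBD patients, rests wholly on assumed risks of 5% to 30%.

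A reader might also infer that counting events would let the trial show the diet to be safe, or the titration advice to work. It would not. The intervals and power above are too weak for a claim of safety or a formal comparison, and no arm receives the diet without titration advice. What the trial would gain is a description of hypoglycaemia and medication changes to set beside the efficacy results. The improvement is cheap and should be made. If the flowchart or Appendix A already provides for such a record, what remains is to name the outcome and its summary.

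**What to change.** 1. Add hypoglycaemia as a named safety outcome, with an event definition fixed before recruitment.
2. Collect it identically in both arms: one event log plus the meter readings, brought with the food diary at weeks 6 and 12. Limit ascertainment to these common visits so that unequal contact does not drive the counts.
3. Record changes in glucose-lowering drugs on the same form.
4. Report descriptively by arm the patients with at least one event and the events per patient-week, with exact 95% intervals, beside the primary outcomes. Repeat events cluster within patients, so the interval for the patient proportion is the more trustworthy. State that no safety claim or formal between-arm test is intended.
5. Reconcile the two follow-up visits in the Study Protocol section with the nine and seven reimbursed visits in the budget.

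The cost is an outcome entry, a definition, one log sheet and a little more data entry; meters, strips and both visits are already planned. Some detection difference between arms may remain. No titration or rescue rule is proposed; those are for the sponsor and investigators.
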